5.1. Treatment Conditions

For both conditions, virtual group formats have been created and will involve adaptations of child activities to virtual sessions. Parent groups will be held prior to groups instead of concurrently to allow added staffing required to prompt and maintain engagement during virtual interventions. If groups are held in session during COVID-19 pandemic conditions, clinic policies for sanitation, PPE, and distancing will be followed for both parent and child groups.

Cognitive Behavioral Intervention for social cognitive deficits: ION-ASD

ION-ASD will be adapted from the manual established in the prior RCT of Seaver-NETT¹⁶. The NETT curriculum is manualized and anchored in CBI strategies, such as problem identification, affective education, performance feedback, and weekly homework activities to facilitate generalization. Each child group session follows a consistent written schedule; uses structured teaching to break down important elements of gestural

Confidential

Rush University Medical Center

communication, nonverbal synchrony, emotional expression, and interpretation of intent; and introduces games and activities to practice each skill. A reinforcement system is used to reinforce participation and spontaneous skill use. The approach to the parent group is psychoeducational with a focus on reviewing skills, rationale for teaching target skills, homework, progress or obstacles, and planning for generalization. Parent groups will also be used to schedule individual meetings with study physicians to review safety and other concerns related to study drug administration. The first three sessions focus on nonverbal communication, and include activities that promote active listening and social referencing (i.e., following eye gaze, gestural communication). The second four-week module targets emotion recognition in the self and others, including a review of basic and complex emotions, and a focus on increasing children's lexicon of emotion words. Children are encouraged to use an awareness of their own emotions to empathize with others and find appropriate ways to respond. The last four-week module focuses on theory of mind, including and taking someone else's perspective and understanding the communicative intent behind nonliteral remarks, building upon skills taught in the emotion recognition module.

Oxytocin will be administered in an intranasal format using the synthesized peptide oxytocin in a solution formulated to promote absorption through the nasal mucosa. Intranasal oxytocin (OXT) will be administered at a dose of 24 IU (3 puffs per nostril), four times per week during the 12-week intervention. The first dose will be administered before the group session at week 1. One administration will occur 30 minutes prior to the weekly social skills group therapy session, and the other three administrations will occur 30 minutes prior to at-home homework/practice sessions. Parents and participants will undergo training modeled after SOARS-B procedures (e.g. parent medication administration handout, in-vivo practice with placebo). If groups are conducted virtually, medication will be mailed to families. Regardless if the group is virtual or in-person participant and guardian will be required to meet with study physician and study PI to review how to properly administer the medication. This review can occur virtually, if needed.

Control Condition: Facilitated Play

The facilitated play condition was manualized for use in the R21 and is a child-directed social play group. Therapists tailor available activities based on interests and abilities of group members. Standard educational practices for children with ASD including visual supports, schedules, and short-directed statements are also used. The concurrent parent group is supportive in nature. Groups will be led by doctoral level clinicians trained in eclectic therapeutic approaches (e.g. supportive psychodynamic). The treatment manual described methods to tailor child-directed play based on the interests and abilities of group members. Therapists established "stations" to support object play (e.g. legos, board games), motor/tactile (e.g., drawing), and dramatic play. The treatment manual also provided instruction on use of reflective statements to foster communication with the child and between peers. Each group session began with a review of a posted visual schedule, a check-in circle, activity-time, and wrap-up. The 30-minute concurrent parent group was supportive in nature and facilitated by the lead therapist.

Confidential

Rush University Medical Center

[figure not shown]

Figure 3. ION: Weekly study procedures

5.2. Study Procedures

Screening Visit(s)

Participants and their parent(s)/legal guardians will come in to sign informed consent and meet with a study clinician to establish eligibility. The following measures will be obtained: a diagnostic assessment, including the ADOS-2 (if required) and DSM-V interview, the ADI-R (if required), a cognitive assessment (WASI-II, KBIT, or WISC-V, if required), the ABC, the CGI-S (Global and Social), the AE rating form, height, weight, vital signs, temperature, a physical examination, review of medical and psychiatric health and concomitant therapies, and a pregnancy test (if applicable). The ADOS-2 (if required) will be video recorded. The screening visit is anticipated to take approximately 4-6 hours to complete. The visit can be split into two visits if this is better for the participant and may be combined with the baseline visit to facilitate scheduling and compliance with visit windows. If required, the following measures can be completed virtually: consenting, DSM-V interview, ADI-R, CARS2, the ABC, the CGI-S (Global and Social), the AE rating form, review of medical and psychiatric health and concomitant therapies.

ECG and safety lab assessments will be completed no more than 30 days before the first dose of medication is administered.

In addition, a physical exam will be conducted, and height, weight, temperature, and vital signs will be obtained. At the baseline visit, the participant will also be randomized to receive either ION-ASD or control (social play), and the research pharmacy will be notified by research staff to dispense a two week supply of study drug to families assigned to ION-ASD. Blood work will be collected prior to participants taking their first dose of study medication. The randomization form will be developed prior to screening/recruitment for each cycle and present randomization schema for 10-12 participants each time. Coordinators will open the Randomization form after the completion of baseline assessments.

Screening and baseline procedures may be combined to accommodate participant schedules.

Baseline Visit(s)

Participants entering the study will undergo the baseline assessments, which are anticipated to take approximately 6-10 hours to complete no more than 21 days from the last screening visit. The visit can be split into as many as three visits if this is better for the participant. The following measures will be completed: the CGI-S (Global and Social), AE rating form, the RMET, the CASI-5, the RBS-R, the SRS, the BASC-3, the PDDBI-SV, the Griffith Empathy Scale, the Children's Communication Checklist, the Caregiver Strain, the DANVA2, the TAT, and the Test, GEMEP emotion recognition test, and sensor-based social-communication monitoring tests..

Vineland Scales of Adaptive Functioning (3rd edition): The VABS-3 is a survey administered to a parent or caregiver is organized around four Behavior Domains: Communication, Daily Living Skills, Socialization, and Motor Skills. The VABS-3 will take the parent/caregiver/LAR approximately 20-60 (average 30) minutes to complete, depending on the subject's age and level of functioning.

Weekly Visits (1-11)

Interventions are delivered in 12-session modules occurring on a weekly basis. Groups will commence when all participants in a cycle have completed baseline evaluations and within 21 days of participant's last baseline visit. Participants will receive group treatment conditions as described in Section 5.1 (Treatment Conditions). Participants randomized to ION will also be prescribed 24 IU (3 puffs/nostril) of intranasal oxytocin 4 times/week to be administered by the parent 30-minutes prior to homework practice (3 x/week) and 30 minutes prior to each weekly group session.

Safety ratings during group: Weeks 1, 3, 5, 7, 9, 11 (or biweekly schedule depending on group start day/date)

Vital signs, temperature, and AE ratings will be completed in 6/12 sessions by a licensed physician on participants in all groups. In addition, the CGI-I (Global and Social) will be completed by the Study clinician. At

Confidential

Rush University Medical Center

Week 6, the CY-BOCS, the CASI-5, the RBS-R, the PDDBI-SV, the Griffith Empathy Scale, the Children's Communication Checklist, the Caregiver Strain and the ABC will be completed. In addition, a two week supply of study drug will be dispensed at weeks 1, 3, 5, 7, 9, 11. Unplanned visits will be permitted if there are any concerns about AEs. Safety visits are expected to take 15-20 minutes.

Week 6 (Midpoint)

Caregiver reports on the ABC, PDDBI-SV, Griffith Empathy Scale, Children's Communication Checklist, CASI-5, Caregiver Strain, Vineland 3, SRS-2, RBS-R, and AIM will be collected at midpoint along with CGI-I ratings (blinded). Ratings may be conducted +/- 7 days from week 6 group depending on family schedules.

Week 12 (Endpoint)

The end of treatment visits occurs at Week 12 (to take place within \pm 7 days from the target date). At these visits, blood work, vital signs, temperature, height, weight, and an ECG will be completed. In addition, participants will undergo a series of assessments, which are anticipated to take approximately 4-6 hours to complete. The visit can be split into as many as three visits if this is better for the participant. The following measures will be completed: the CGI-I (Global and Social), the AE rating form, the Bates & Reilly Conversational Task, the CY-BOCS, Let's Face It, the RMET, the CASI-5, the RBS-R, the SRS, the ABC, the BFRT, the BASC-3, the PDDBI-SV, the Griffith Empathy Scale, the CCC, the Caregiver Strain, the DANVA2, the TAT, , and the GEMEP emotion recognition test, and sensor-based social-communication monitoring tests.

Week 16 & Week 24 (Maintenance visits 1 & 2)

There will be an additional follow-up appointment 12 weeks (\pm 7 days) after the participant stops taking the study drug. This visit is primarily to examine safety of OXT discontinuation, and look for possible maintenance of any favorable effects of ION-, and longer term safety. The assessments completed during this visit are identical to the Week 12/end of treatment visit.

Termination Visit: A participant may voluntarily withdraw from the study at any time. The PI has the right to discontinue a subject from this study or withdraws a participant from the study at any time. Every effort will be made to obtain information on subjects who withdraw. Participants who discontinue study drug prematurely will be asked to return to the clinic and complete all end of study safety lab work (week 12 blood work).

Participants will also be asked to complete all endpoint study procedures on their final visit before withdrawal to allow for true intent to treat analysis.

Missed Visits and Visit Windows

Subjects that miss a weekly group meeting will be asked to come in +/-2 days from the scheduled day to complete safety assessments. In the event the subject is unable to come in, we will ask the family to follow up with the study physician via phone to complete safety assessments.

Video Recording & Electronic Assessment

The ADOS-2 will be recorded during the study to ensure reliability. Additionally both the facilitated play and cognitive behavioral social skills groups will also be video recorded.

Additionally some tasks will be presented on a computer in electronic format including: DANVA2, Reading Mind in Eyes, TAT and GEMEP Emotion Recognition Test. Data will be captured, labeled with participant ID, and stored on the encrypted Rush network. The following assessments will be video recorded and eye tracking data will be recorded using the Tobii T-60 eye-tracker: CGI-S, CGI-I, Reading Mind in Eyes, DANVA2, TAT, and . Recordings will be used to analyze response time, attention to social regions of stimuli, and engagement with the examiner. The recording will be labeled with a code number, stored electronically on the encrypted Rush network in a password protected folder and destroyed when the study is completed. Sensor-based measures of social-communication will utilize a computer-based package and three system components: wearable eye-tracking device (e.g. Tobii glasses), 3-D cameras, and audio recordings of voice recognition software to automatically detect target social behaviors including eye-gaze, facial expressions, use of emotion

Confidential

Rush University Medical Center

words, quality of speech, and gestural communication. These tools will be used to record target behaviors during CGI ratings by the Independent Evaluator at BL, Weeks 2, 6, 12 and, 16- & 24- week follow-up. Data recorded from these measures will be labeled and stored electronically on a secure server.

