3.1. Study Design

This is a two-phase, 3 year, randomized, single-blind, parallel group, contact controlled pilot trial of OXT augmentation of CBI groups in youth with ASD. Phase 1 (n=10) is an initial development trial to refine manuals, procedures, and outcome evaluations. Phase 2 (n=70) will evaluate feasibility, safety, and preliminary efficacy of ION-ASD relative to the contact control (i.e. social play group). All participants are expected to be outpatients and will participate in a 12-session group therapy, with a follow-up study visit at 24 weeks. Evaluations will be conducted at four time points: Screening, Baseline, Endpoint (week 12), and Follow-up (1-month & 3-months post-treatment).

Each phase will randomly assign in a 1:1 ratio to either ION-ASD or control in blocks of 10. Efficacy outcomes will be evaluated by both caregiver report and blinded independent evaluators (IE); safety assessments will be conducted by unblinded treating medical clinicians (Medical TC). Caregivers and participants will be instructed to conceal group assignment from IEs. IEs, participants, and caregivers will also be instructed on reporting strategies should group assignment be revealed. Corrective action plans in these scenarios will be employed if necessary and include changing IE raters and flagging data. IEs will be asked to “guess” patient conditions at the end of the trial to evaluate integrity of the blind.

Medical TCs will monitor side-effects using weekly ratings with the participant and caregiver. Clinical IEs will evaluate global functioning and social communication skills. Neurocognitive IEs will conduct blinded neurocognitive assessments (see Appendix A: Time & Events Schedule).

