8.9. Sample size considerations

Based on data from the NETT trial, published trials in sustained OT treatment⁵⁴, and single-dose challenge studies in autism⁴⁹ we expect our sample size (n=25/group with 5% attrition) to yield 80% power to detect a difference in means of 0.40, assuming a standard deviation of differences of 0.670, with a 0.050 two-sided significance level. Although potentially underpowered, we believe data from this trial will provide important information on safety, tolerability, and treatment targets from a novel, multi-dosing OT-combined treatment strategy. Specific Aim 2 (treatment targets, pre-treatment factors predictors). Repeated measures ANOVAs will be conducted to evaluate group differences on social behavior and social cognition composites, social recognition, mental state inference, affiliation, social reward and social competence (i.e. SSIS) in order to identify potential treatment targets for the combined treatment approach. Factors predicting treatment response will include global scores on all baseline measures. Responder status will be entered as a categorical variable as defined above (CGI-I≤2 + SSIS > 25%). PCA will be conducted on significant baseline predictors to develop composite variables and used to predict response using logistic regression.

Confidential

Rush University Medical Center

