Data Analysis. Primary: Composite scores of both primary outcomes (i.e., SBI and SC) will be used as the response (i.e., outcome) variable in a series of mixed-effects linear regression models using the *lmer* package in *R Studio* to assess the effect of treatment condition (ION-ASD vs. Facilitated Play), time (e.g., change from baseline after 12 weeks), and condition X time interaction. Across all models, the individual participant will be included as the random effect. Age, verbal IQ, ADHD and generalized anxiety (from the Child & Adolescent Symptom Inventory-5 [CASI-5] T-scores) will be entered into the model to be examined as potential covariates and/or moderators to outcomes as in prior work. We will estimate effect sizes (standardized Betas) and confidence intervals (95%) acknowledging the likelihood that analyses may not permit definitive conclusions given the likely size of the confidence intervals. Finally, if the statistical assumptions of the model are not met (e.g., homoscedasticity, normality, linear relationships), generalized linear models with appropriate link functions or potential transformations of predictor variables will be assessed.

Secondary Outcomes. The linear mixed-effects models will also be used on secondary outcome measures: SRS T-score, mean Caregiver Strain Global rating scale. Responder (i.e., Clinical Global Inventory-Improvement [CGI-I]) analysis will be conducted using either a Chi-squared or Fisher's exact test (when observations are small such that $>20\%$ of cells have *expected* count <5) on the number of responders (i.e., CGI-I scores of 1-2) versus non-responders (i.e., CGI-I scores of 5-7) by group.

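### The primary model leaves out both the cycle children are randomised within and the group they are treated in, so the Week 12 interval may be too wide or too narrow

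*Protocol*

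**What the plan says.** **Allocation.** Protocol 3.1 assigns children 1:1 "to either ION-ASD or control in blocks of 10". Protocol 5.2 (Screening Visits) has a form drawn up before each cycle to "present randomization schema for 10-12 participants each time". Under Weekly Visits, 5.2 starts the groups once every child in the cycle has finished baseline. Children are therefore randomised individually within cycles, and both arms of a cycle begin together.

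**Delivery.** Both conditions are given in groups. For both, Protocol 5.1 says that "virtual group formats have been created and will involve adaptations of child activities to virtual sessions", and it allows groups to be virtual or in person. It sets no date or rule for a switch.

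**Analysis.** Protocol 8.8 models the composites on condition, time and their interaction. The SAP (Data Analysis, Primary) uses the same three terms with participant as the only random effect. It lists "Age, verbal IQ, ADHD and generalized anxiety" as possible covariates or moderators. Neither document puts cycle, block, therapy group or delivery format in the model.

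**The concern.** When allocation is balanced within a block, differences in mean change between blocks cancel from the arm contrast. If the block is not modelled, those differences stay in the residual variance and the standard error is larger than it need be. Cycles run at different times and possibly in different formats, so some variation in change between them is plausible. Protocol 8.9 concedes that the trial may be underpowered, so precision already built into the design should not be lost.

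The same omission has a second side. With 10 to 12 children per cycle split 1:1, about 5 or 6 are treated together in each arm. If they share a group effect (therapist, peers, attendance), that effect does not cancel from the arm contrast, and the planned standard error is too small. What is at stake is whether the Week 12 interval has its stated coverage.

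**Working it through.** **1. The plan's own figure.** Protocol 8.9 expects the sample to "yield 80% power to detect a difference in means of 0.40". Its other inputs are 25 children per arm less 5% dropout, an SD of 0.670 for the differences, and a two-sided test at 0.05. A paired (one-sample) t test reproduces this: with n = 24 (25 less 5%), SE = 0.670/√24 = 0.137 and power is 80.0%. As a comparison of two arms of 24 or 25, SE = 0.670 × √(2/n) and power is only about 53 to 56% (t or normal calculation). That mismatch is a separate point. Here 0.670 is taken as the SD of change.

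**2. Inputs.** Phase 2 has 70 children (Protocol 3.1), taken as 7 cycles of 5 per arm with no dropout and one therapy group per arm and cycle. The shares of the variance of change due to cycle (c) and therapy group (g) are assumptions; the documents give neither.

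**3. Cycle only (g = 0).**
- Without cycle: SE = 0.67 × √(2/35) = 0.1602, 68 df, half-width 1.995 × 0.1602 = 0.320.
- With cycle: SE = 0.1602 × √(1 − c), 62 df, t = 1.999.
- Power with cycle is from the noncentral t with noncentrality 0.40/SE. Type I error and power without cycle are simulated (40,000 trials per row).

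| c | Half-width with cycle | Excess width without cycle | Type I error without cycle | Power without / with cycle |
|---|---|---|---|---|
| 0 | 0.320 | −0.2% | 5.1% | 69% / 69% |
| 5% | 0.312 | 2.4% | 4.6% | 70% / 71% |
| 10% | 0.304 | 5.2% | 4.1% | 71% / 74% |
| 20% | 0.286 | 11.6% | 3.2% | 72% / 79% |

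The excess widths are practically the same at N = 50, 80 and 90; only the absolute widths change (0.381, 0.298 and 0.281 without cycle).

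**4. Which term.** The participant random intercept and the change contrast already remove stable differences in level between cycles. In a mixed-model check at c = 10% (40 simulated datasets), the mean SE of condition-by-time was 0.1592 with no cycle term, 0.1592 with a cycle main effect and 0.1514 with cycle-by-time. Only the interaction recovers precision.

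**5. Adding a therapy-group effect.** The true variance of the arm difference is (2 × 0.67²/35) × (1 − c + 4g). The planned analysis estimates on average (2 × 0.67²/35) × [1 − (4/34)(c + g)]. Setting the two equal gives 4.118g = 0.882c, so g = 0.21c. Once the therapy-group share exceeds about a fifth of the cycle share, the planned interval is too narrow.

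| c | g | Type I error as planned | With cycle alone |
|---|---|---|---|
| 0 | 5% | 7.5% | 7.8% |
| 5% | 5% | 6.8% | 7.8% |
| 10% | 5% | 6.3% | 7.8% |
| 20% | 5% | 5.2% | 8.1% |
| 5% | 10% | 9.4% | 10.8% |
| 10% | 10% | 8.8% | 11.1% |

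A paired t analysis of the 7 within-cycle arm differences (6 df) holds type I error at about 5% in every row. At c = 10%, g = 5% its mean half-width is 0.395, against 0.316 as planned.

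**6. Block and cycle.** A cycle of 12 filled from blocks of 10 takes one whole block and two places from the next. If both places fall to one arm, the cycle splits 7:5, and the next cycle begins mid-block. Block and cycle are then no longer the same unit.

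**The case against.** The strongest case against is that the gain is modest and rests on a variance that nobody has stated. At a 5% cycle share it is about one point of power, in a self-described pilot whose SAP already expects inconclusive intervals. That stands, and it limits the weight of the point.

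A reader might infer that the Week 12 interval is simply too wide and the test conservative. The documents do not support this. They show no cycle variation in change, and treatment in groups creates an effect in the other direction that a small therapy-group share is enough to make dominant. Adding cycle alone could then make the primary test less valid.

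A reader might also infer that moving from in-person to virtual delivery between cycles distorts the comparison. Protocol 5.1 permits either format but schedules no change and does not fix format within a cycle. If a change did fall between cycles, it would be common to both arms and would not bias the arm contrast.

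The cost in parameters is also real. With four time points and 7 cycles, cycle and cycle-by-visit add 6 + 18 = 24 coefficients. A baseline-adjusted Week 12 model needs only 6. None of this is a reason to leave the randomisation factor unaddressed.

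**Conclusion.** The point holds in conditional form. Children are randomised within cycles and treated in groups, and the primary model represents neither. The excess widths of about 2, 5 and 12% apply only if cycle explains 5, 10 or 20% of the variance of change and there is no therapy-group effect. With a 5% group share and a cycle share of 5 to 10%, the planned test instead runs at about 6 to 7% and cycle alone takes it to about 8%. All figures assume equal cycles of 10, complete data and an SD of change of 0.67. The net direction cannot be settled from the documents. The change should be made because it is cheap before the data are seen, and becomes a discretionary choice afterwards.

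**What to change.** 1. Define the cycle as the randomisation block, and reconcile the blocks of 10 in Protocol 3.1 with the 10 to 12 children per form in Protocol 5.2.
2. In Protocol 8.8 and the SAP's primary analysis, prespecify cycle with cycle-by-visit, or cycle in a baseline-adjusted Week 12 model.
3. In the same sentence, add a therapy-group (arm-by-cycle) random effect on change, or small-sample cluster-robust inference. Do not add cycle alone.
4. Record each group's delivery format and report results by format descriptively only.

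The cost is a few sentences and about 6 or 7 degrees of freedom for cycle at each visit (7 or 8 cycles). Allowing for therapy group will probably widen the interval. In the paired analysis above it goes from 0.316 to 0.395, about 25% wider (0.395/0.316 = 1.25). That is the price of correct coverage with so few groups.
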